7.2. Laboratory Evaluations

Laboratory data collected during the study will be analyzed and summarized using both quantitative and qualitative methods. Summaries of laboratory data will be provided for the Safety Analysis Set and will include data collected up to the last dose of any study drug plus 30 days for subjects who have permanently discontinued study drug, or all available data at the time of the database snapshot for subjects who were ongoing at the time of an interim analysis. The analysis will be based on values reported in conventional units. When values are below the LOQ, they will be listed as such, and the closest imputed value will be used for the purpose of calculating summary statistics as specified in Section 3.7.

A baseline laboratory value will be defined as the last nonmissing measurement obtained on or prior to the date/time of first dose of any study drug.

For placebo subjects who were then re-randomized, the baseline laboratory value for the re-randomization period will be the last available measurement obtained on or prior to the date/time of first dose of filgotinib. The lab abnormalities after the first dose of filgotinib will be assessed from the baseline of the re-randomization period.

A by-subject listing for laboratory test results will be provided by subject ID number and visit in chronological order for hematology, serum chemistry, and urinalysis separately. Values falling outside of the relevant reference range and/or having a severity grade of 1 or higher on the CTCAE severity grade will be flagged in the data listings, as appropriate.

No formal statistical testing is planned.

7.2.1. Summaries of Numeric Laboratory Results

Descriptive statistics of Baseline values, values at each postbaseline visit and change from Baseline at each postbaseline visit will be provided by treatment group for the following laboratory tests:

- Hematology
 - Hematocrit
 - Hemoglobin
 - Platelet count
 - Red blood cell count
 - White blood cell (WBC) count
 - Mean corpuscular volume
 - Lymphocytes

- Monocytes
- Neutrophils
- Eosinophils
- Basophils
- Chemistry
 - Alanine aminotransferase (ALT)
 - Aspartate aminotransferase (AST)
 - Alkaline phosphatase (ALP)
 - Total bilirubin
 - Serum creatinine
 - Creatinine clearance by Cockcroft-Gault formula
 - Creatinine phosphokinase (CPK)
 - Glucose
- Lipid
 - Triglycerides
 - Total cholesterol
 - HDL
 - LDL
 - LDL/HDL ratio

Change from baseline to a postbaseline visit will be defined as the visit value minus the baseline value. The mean, median, Q1, Q3, minimum, and maximum values will be displayed to the reported number of digits; SD values will be displayed to the reported number of digits plus 1.

Median (Q1, Q3) of the observed values for the laboratory tests specified above will be plotted using a line plot by treatment group and visit.

In the case of multiple values in an analysis window, data will be selected for analysis as described in Section 3.8.3.

7.2.2. Graded Laboratory Value

The CTCAE Version 4.03 will be used to assign toxicity grades (0 to 4) to laboratory results for analysis. Grade 0 includes all values that do not meet the criteria for an abnormality of at least Grade 1. For laboratory tests with criteria for both increased and decreased levels, analyses for each direction (ie, increased, decreased) will be presented separately.

7.2.2.1. Treatment-Emergent Laboratory Abnormalities

Treatment-emergent laboratory abnormalities are defined as values that increase at least 1 toxicity grade from baseline at any postbaseline time point, up to and including the date of last dose of any study drug plus 30 days for subjects who permanently discontinued study drug, or the last available date in the database snapshot for subjects who were still on treatment at the time of an interim analysis.

For placebo subjects who were then re-randomized, treatment-emergent laboratory abnormalities of placebo period are defined as values that increase at least 1 toxicity grade from the baseline at any postbaseline time point, up to and including the first dose date of filgotinib. Treatment-emergent laboratory abnormalities of re-randomized period are defined as values that increase at least 1 toxicity grade from the new baseline after Week 24 at any postbaseline time point, up to and including the date of last dose of any study drug plus 30 days, or the last available date in the database snapshot for subjects who were still on treatment at the time of an interim analysis.

Placebo subjects who were not re-randomized have treatment-emergent laboratory abnormalities in the placebo period which are defined as values that increase 1 toxicity grade from the baseline at any postbaseline time point, up to and including the date of last dose of any study drug plus 30 days.

If the relevant baseline laboratory value is missing, any abnormality of at least Grade 1 observed within the time frame specified above will be considered treatment emergent.

7.2.2.2. Treatment-Emergent Marked Laboratory Abnormalities

Treatment-emergent marked laboratory abnormalities are defined as values that increase from baseline by at least 3 toxicity grades at any postbaseline time point, up to and including the date of the last dose of any study drug plus 30 days for subjects who permanently discontinued study drug or the last available date in the database snapshot for subjects who were still on treatment at the time of an interim analysis.

For placebo subjects who were then re-randomized, treatment-emergent marked laboratory abnormalities of placebo period are defined as values that increase from baseline by at least 3 toxicity grades at any postbaseline time point, up to and including the first dose date of filgotinib. Treatment-emergent marked laboratory abnormalities of re-randomized period are defined as values that increase from the new baseline after Week 24 by at least 3 toxicity grades at any postbaseline time point, up to and including the date of last dose of any study drug plus 30 days, or the last available date in the database snapshot for subjects who were still on treatment at the time of an interim analysis.

Placebo subjects who were not re-randomized have treatment-emergent marked laboratory abnormalities in the placebo period which are defined as values that increase from baseline by at least 3 toxicity grades at any postbaseline time point, up to and including the date of last dose of any study drug plus 30 days.

If the relevant baseline laboratory value is missing, any Grade 3 or higher values observed within the time frame specified above will be considered treatment-emergent marked abnormalities.

7.2.2.3. Summaries of Laboratory Abnormalities

Laboratory data that are categorical will be summarized using the number and percentage of subjects in the study with the given response at baseline and each scheduled postbaseline visit.

The following summaries (number and percentage of subjects) for treatment-emergent laboratory abnormalities will be provided by laboratory test and treatment group; subjects will be categorized according to the most severe postbaseline abnormality grade for a given laboratory test:

- Graded laboratory abnormalities
- Grade 3 or higher laboratory abnormalities
- Marked laboratory abnormalities

For all summaries of laboratory abnormalities, the denominator is the number of subjects with nonmissing postbaseline values up to 30 days after last dosing date.

A by-subject listing of treatment-emergent Grade 3 or higher laboratory abnormalities and marked laboratory abnormalities will be provided separately by subject ID number and visit in chronological order. These listings will include all test results that were collected throughout the study for the laboratory test of interest, with all applicable severity grades or abnormal flags displayed.

7.2.3. Laboratory Evaluations of Special Interest

7.2.3.1. Liver-Related Laboratory Evaluations

Liver-related abnormalities after initial study drug dosing will be examined and summarized using the number and percentage of subjects who were reported to have the following laboratory test values for postbaseline measurements:

- AST: (a) > 3 times of the upper limit of reference range (ULN); (b) > 5 x ULN; (c) > 10 x ULN; (d) > 20 x ULN
- ALT: (a) > 3 x ULN; (b) > 5 x ULN; (c) > 10 x ULN; (d) > 20 x ULN
- AST or ALT > 3 x ULN and total bilirubin > 2 x ULN

The summary will include data from all postbaseline visits up to 30 days after the last dose of any study drug. For individual laboratory tests, subjects will be counted once based on the most severe postbaseline values. For both the composite endpoints of AST or ALT and total bilirubin, subjects will be counted once when the criteria are met at the same postbaseline visit date. The denominator is the number of subjects in the Safety Analysis Set who have nonmissing postbaseline values of all relevant tests at the same postbaseline visit date. A listing of subjects who met at least 1 of the above criteria will be provided.

7.2.3.2. Complete Blood Count-Related Laboratory Evaluations

Complete blood count (CBC)-related abnormalities such as anemia, leucopenia, neutropenia, lymphopenia, and thrombocytopenia after initial study drug dosing will be examined and summarized using the number and percentage of subjects who were reported to have the following laboratory test values for postbaseline measurements:

- Hemoglobin: (a) any postbaseline worsening CTCAE grade from baseline; (b) baseline value of less than Grade 3 and increase to Grade 3 or higher at worst postbaseline; (c) baseline value of less than Grade 3 and increase to Grade 4 at worst postbaseline
- WBC count: (a) any postbaseline worsening CTCAE grade from baseline; (b) baseline value of less than Grade 3 and increase to Grade 3 or higher at worst postbaseline; (c) baseline value of less than Grade 3 and increase to Grade 4 at worst postbaseline
- Absolute neutrophil count: (a) any postbaseline worsening CTCAE grade from baseline; (b) baseline value of less than Grade 3 and increase to Grade 3 or higher at worst postbaseline; (c) baseline value of less than Grade 3 and increase to Grade 4 at worst postbaseline

- Lymphocyte count: (a) any postbaseline worsening CTCAE grade from baseline; (b) baseline value of less than Grade 3 and increase to Grade 3 or higher at worst postbaseline; (c) baseline value of less than Grade 3 and increase to Grade 4 at worst postbaseline
- Platelet count: (a) any postbaseline worsening CTCAE grade from baseline; (b) baseline value of less than Grade 3 and increase to Grade 3 or higher at worst postbaseline; (c) baseline value of less than Grade 3 and increase to Grade 4 at worst postbaseline

The summary will include data from all postbaseline visits up to 30 days after the last dose of any study drug.

7.3. Body Weight and Vital Signs

Descriptive statistics will be provided by treatment group for body weight, BMI and vital signs (systolic and diastolic blood pressures [mmHg], pulse [beats/min]) as follows:

- Baseline value
- Values at each postbaseline visit
- Change from baseline at each postbaseline visit

A baseline value will be defined as the last available value collected on or prior to the date/time of first dose of any study drug.

For placebo subjects who were then re-randomized, the baseline value for re-randomization period will be defined as the last available value collected on or prior to the date/time of the first dose of filgotinib.

Change from baseline to a postbaseline visit will be defined as the postbaseline value minus the baseline value. Body weight and vital signs measured at unscheduled visits will be included for the baseline value selection.

In the case of multiple values in an analysis window, data will be selected for analysis as described in Section 3.8.3. No formal statistical testing is planned.

A by-subject listing of vital signs (systolic and diastolic blood pressure [mmHg], pulse [beats/min], respiration [breaths/min], and body temperature [°C]) will be provided by subject ID number and visit in chronological order. In the same manner, a by-subject listing of body weight, height, and BMI will be provided separately.

7.4. Prior and Concomitant Medications

Medications collected at screening and during the study will be coded using the World Health Organization (WHO) Drug dictionary version BSEP17.

All the analyses in this section will be performed for general prior /concomitant medications and RA-specific prior/concomitant medications separately, unless otherwise specified.

7.4.1. Prior Medications

Prior medications are defined as any medication taken before a subject took the first study drug.

Prior medications will be summarized by Anatomical Therapeutic Chemical (ATC) drug class preferred name using the number and percentage of subjects for each treatment group and overall. A subject reporting the same medication more than once will be counted only once when calculating the number and percentage of subjects who received that medication. The summary will be provided by preferred name in order of descending overall frequency. For drugs with the same frequency, sorting will be done alphabetically.

For the purposes of analysis, any medication with a start date prior to the first dosing date of any study drug will be included in the prior medication summary regardless of when the stop date is. If a partial start date is entered the medication will be considered prior unless the month and year (if day is missing) or year (if day and month are missing) of the start date are after the first dosing date. Medications with a completely missing start date will be included in the prior medication summary, unless otherwise specified.

Summaries will be based on the Safety Analysis Set. No formal statistical testing is planned.

7.4.2. Concomitant Medications

Concomitant medications are defined as medications taken while a subject took study drug. Use of concomitant medications will be summarized by ATC drug class preferred name using the number and percentage of subjects for each treatment group. A subject reporting the same medication more than once will be counted only once when calculating the number and percentage of subjects who received that medication. The summary will be provided by preferred term in descending overall frequency. For drugs with the same frequency, sorting will be done alphabetically.

For the purposes of analysis, any medication with a start date prior to or on the first dosing date of any study drug and continued to take after the first dosing date, or started after the first dosing date but prior to or on the last dosing date of study drug will be considered concomitant medications. Medications started and stopped on the same day as the first dosing date or the last dosing date of any study drug will also be considered concomitant. Medications stopped on the same day as the first dosing date will be considered concomitant. Medications with a stop date prior to the date of first dosing date of any study drug or a start date after the last dosing date of any study drug will be excluded from the concomitant medication summary. If a partial stop date is entered, any medication with the month and year (if day is missing) or year (if day and month are missing) prior to the date of first study drug administration will be excluded from the concomitant medication summary. If a partial start date is entered, any medication with the month and year (if day is missing) or year (if day and month are missing) after the study drug stop date will be excluded from the concomitant medication summary. Medications with completely missing start and stop dates will be included in the concomitant medication summary, unless otherwise specified.

For placebo subjects who were then re-randomized, concomitant medication with a start date prior to the first dose date of filgotinib will be allocated to the placebo controlled period. Concomitant medication with a start date on or after first dose date of filgotinib will be allocated to the re-randomized period.

For placebo subjects who were then re-randomized, a concomitant medication with incomplete start date that is prior to the month and year (or year) of the first dose date of filgotinib will be allocated to the placebo controlled period. A concomitant medication with incomplete start date that is after the month and year (or year) of the first dose date of filgotinib will be allocated to the re-randomized period.

In addition, an concomitant medication with completely missing start date or incomplete start date that is same as the month and year (or year) of the first dose date of filgotinib, and stop date that is prior to the date (or month and year if day is not recorded; or year alone if month is not recorded) of the first dose of filgotinib will be allocated to the placebo controlled period. An concomitant medication with completely missing start date or incomplete start date that is same as the month and year (or year) of the first dose date of filgotinib, and stop date that is missing, or the same as, or after the date (or month and year if day is not recorded; or year alone if month is not recorded) of the first dose of filgotinib will be allocated to the re-randomized period

Summaries will be based on the Safety Analysis Set. No formal statistical testing is planned.

All prior and concomitant medications (other than per-protocol study drugs) will be provided in a by-subject listing sorted by subject ID number and administration date in chronological order.

7.5. Electrocardiogram Results

7.5.1. Investigator Electrocardiogram Assessment

A shift table of the investigators' assessment of ECG results at each visit compared with baseline values will be presented by treatment group using the following categories: normal; abnormal (not clinically significant); abnormal (clinically significant); or missing. The number and percentage of subjects in each cross-classification group of the shift table will be presented. Subjects with a missing value at baseline or postbaseline will not be included in the denominator for percentage calculation.

No formal statistical testing is planned.

A by-subject listing for ECG assessment results will be provided by subject ID number and visit in chronological order

7.6. Other Safety Measures

A data listing will be provided for subjects who become pregnant during the study.

7.7. Changes From Protocol-Specified Safety Analyses

There are no deviations from the protocol-specified safety analyses.

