Blood samples for biomarker analysis should be collected at Day 1, Weeks 4, 8, 12, 24, 36, and Week 52 or ET and urine samples should be collected at Day 1, Weeks 12, 24, and Week 52 or ET.

Radiographs of the bilateral hands, wrists, and feet should be taken at Screening, Weeks 12, 24, and Week 52 or ET. However, if a subject prematurely discontinues study participation and has had X-rays performed within the previous 12 weeks, then X-rays do not need to be repeated at the ET visit. Radiographs after enrollment may be done +/- 7 days of the scheduled visit. Post treatment follow-up assessments include AEs, concomitant medications, physical examination, 12-lead ECG, weight, vital signs, blood and urine sampling for safety laboratory tests, and urine pregnancy tests (females of child bearing potential only).

CCI

CCI

Test Product, Dose, and Mode of Administration:

200 mg filgotinib orally q.d.
100 mg filgotinib orally q.d.

Reference Therapy, Dose, and Mode of Administration:

Adalimumab injection (40 mg s.c.) or PTM s.c. q2w
PTM filgotinib 200 mg orally q.d.
PTM filgotinib 100 mg orally q.d.

Required Background Medication:

Stable prescription of weekly MTX as described in the inclusion criteria and administered according to the local product label/standard of care.

Criteria for Evaluation:

Safety:

Safety will be assessed by documentation of AEs, clinical laboratory tests, physical examinations, vital signs, and 12-lead ECGs during the study.

Efficacy: The primary endpoint is the proportion of subjects who achieve an ACR20 response at Week 12.

The key secondary endpoints are:

- The proportion of subjects who achieve DAS28 (CRP) \leq 3.2 at Week 12
- Change from Baseline in the HAQ-DI score at Week 12
- The proportion of subjects who achieve DAS28 (CRP) $<$ 2.6 at Week 24
- Change from Baseline in mTSS at Week 24

Pharmacokinetics: Plasma concentrations of filgotinib and its metabolite (GS-829845) will be analyzed.

Statistical Methods: The primary analysis set for efficacy analyses will be the Full Analysis Set (FAS), which includes all randomized subjects who received at least one dose of study drug.

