PK	Pharmacokinetics
PP	per-protocol
PT	prothrombin time
PTM	Placebo to match
q.d.	quaque die ; once daily
RA	rheumatoid arthritis
RF	rheumatoid factor
RR	respiratory rate
SAE	serious adverse event
SAP	Statistical Analysis Plan
SBP	systolic blood pressure
s.c.	Subcutaneous
SD	standard deviation
SDAI	Simplified Diagnostic Activity Index
SF-36	Short-form health survey
SI	International system of units
SJC66	swollen joint count based on 66 joints
SOC	system organ class
STIR	short tau inversion recovery sequence
TB	Tuberculosis
TEAEs	Treatment emergent adverse events
TJC68	tender joint count based on 68 joints
t_{max}	the time of occurrence of maximum observed plasma concentration
TNF α	tumor necrosis factor alpha
TNFi	tumor necrosis factor inhibitors
UGTs	uridine 5'-disphosphate glucuronosyltransferases
ULN	upper limit of normal
US	United States
vfPBMCs	Viably frozen peripheral blood mononuclear cells
vs.	Versus
WBC	white blood cell
WPAI-RA	Work Productivity and Activity Impairment – Rheumatoid Arthritis

Definition of Terms

QTcF QT interval corrected for HR according to Fridericia's formula:

$$QTcF = QT / (RR)^{(1/3)}, \text{ where } RR = 60/HR$$

RR = RR interval in seconds
HR = heart rate in beats per minute

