6.7.7. Other Safety Assessments

6.7.7.1. 12-lead Electrocardiogram

A resting 12-lead ECG should be performed at the time points indicated in the study procedures table ([Appendix 2](#)).

The ECG should be obtained after the subject has been resting in the supine position for 5 min and will include heart rate (HR), inter-beat (RR), QRS, uncorrected QT, morphology, and rhythm analysis. QT interval corrected for HR according to Fridericia (QTcF) will be derived during the statistical analysis. ECGs will be interpreted by the investigator for clinical significance and results will be entered into the eCRF.

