8.6. Safety Analysis

All safety analyses will be performed using the safety analysis set.

Safety will be evaluated by assessment of clinical laboratory tests, physical examinations, vital signs measurements at various time points during the study, and by the documentation of AEs.

All safety data collected on or after the first dose of study drug administration up to 30 days after the last dose of study drug, unless specified otherwise, will be summarized by treatment group according to the study drug received.

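### The protocol assigns the QTcF derivation to the statistical analysis, but the SAP never derives it and declares no change to the safety analyses

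*SAP*

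**What the plan says.** **Protocol.** The synopsis counts ECGs among the safety evaluations: "Safety will be assessed by documentation of AEs, clinical laboratory tests, physical examinations, vital signs, and 12-lead ECGs during the study". Section 6.7.7.1 sets out what each recording contains (it "will include heart rate (HR), inter-beat (RR), QRS, uncorrected QT, morphology, and rhythm analysis") and then says that "QT interval corrected for HR according to Fridericia (QTcF) will be derived during the statistical analysis". The formula is under Definition of Terms: QT divided by the cube root of RR, with RR = 60/HR in seconds. ECGs are scheduled at six points: Screening, Weeks 12, 24 and 36, Week 52 or early termination, and Post Treatment Week 4. Section 8.6, which describes the safety analysis, reads "Safety will be evaluated by assessment of clinical laboratory tests, physical examinations, vital signs measurements at various time points during the study" and adds adverse events. It mentions neither ECG nor QTcF.

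**SAP.** Section 7.5 has a single subsection, 7.5.1. It plans a shift table of what the investigators concluded, worded as "assessment of ECG results at each visit compared with baseline values will be presented by treatment group using the following categories". There are four such groups: a normal tracing, an abnormality judged clinically significant, an abnormality judged not to be, and no reading. A by-subject listing of the ECG assessment results follows. Elsewhere, ECG appears in the abbreviations, the visit windows (3.8.2, Tables 3-7 and 3-8), the record-selection rules (3.8.3, where the examples treat it as normal or abnormal) and one line in 3.8.2 saying that post-treatment ECG data will be summarised. Section 7.7 closes the safety chapter with "There are no deviations from the protocol-specified safety analyses".

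**The concern.** The protocol gives the analysis a task, supplies the formula for it and collects its inputs. The SAP does not carry the task out, and the one place where a reader would look for a declared departure says there is none. The contrast with efficacy is marked: SAP 6.5 itemises each change from the protocol and gives a reason, so a reader will take 7.7 as an equally complete statement.

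A team that follows the SAP exactly would produce no derived QTcF value and no quantitative QT result. The shift table records a clinical judgement made by investigators at roughly 250 to 300 centres. It shows whether tracings were called abnormal, but it cannot estimate a mean change in QTcF by arm. Rate correction has some relevance here: Protocol 1.2.2.2 reports a slight, non-adverse rise in heart rate with the metabolite GS-829845 in nonclinical work at 7 times the clinical peak exposure, and uncorrected QT is hard to read if heart rate moves.

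**Working it through.** This is a consistency check between two documents. The plan states no figure that could be reproduced.

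**1. Is there a commitment?** Yes. Protocol 6.7.7.1 says QTcF *will* be derived and places the derivation in the statistical analysis. The formula is given once, in the Definition of Terms.

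**2. Are the inputs specified for collection?** Yes. HR, RR and uncorrected QT are all named in 6.7.7.1, and ECG results go into the eCRF. The eCRF itself is not among the documents, so whether each interval has its own data field cannot be confirmed.

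**3. Does the SAP carry it out?**

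| Item | Protocol | SAP |
|---|---|---|
| QTcF formula | Definition of Terms | none |
| QTcF derivation | 6.7.7.1 | none |
| QTcF summary or listing | not specified | none |
| Investigator's ECG interpretation | 6.7.7.1 | 7.5.1, shift table and listing |
| Post-treatment ECG | Post Treatment Week 4 visit | 3.8.2, general line, no interval named |
| Declared change to safety analyses | not applicable | 7.7, none |

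Redaction does not explain the gap: the SAP's table of contents shows only 7.5.1 under 7.5.

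**4. What precision would a summary offer?** This is an illustration only. The SD of change in QTcF is not in the documents; 15 to 20 ms is an assumption. For two arms of *n* subjects each, the 95% CI half-width for a difference in mean change is

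1.96 × SD × √(2/n)

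With n = 450, √(2/450) = 0.0667.

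- SD 15 ms: 1.96 × 15 × 0.0667 = 1.96 ms
- SD 20 ms: 1.96 × 20 × 0.0667 = 2.61 ms

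**5. To which visits does that apply?** Week 12 at best. Week 14 non-responders stop study drug, and SAP 3.8.2 limits its ECG visit windows to on-treatment data (up to last dose plus 7 days), so the arms are smaller by Week 24. Remaining placebo subjects are reassigned to filgotinib at Week 24, so Weeks 36 and 52 have no placebo arm.

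**The case against.** The best defence of SAP 7.7 is that it speaks of protocol-specified safety *analyses*, and that these are set out in Protocol 8.6. Section 8.6 names neither ECG nor QTcF, so measured against it the SAP adds an ECG analysis rather than removing one. The QTcF sentence stands in a section on assessments. This narrow reading is open to the sponsor, and it is why 7.7 is better called inconsistent with 6.7.7.1 than simply false. It does not dispose of the point, because 6.7.7.1 itself assigns the derivation to the statistical analysis and the SAP does not perform it under any reading.

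Three further objections are right and limit the point:

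- The protocol promises a derivation, not a table. A reader might infer that planned summaries of mean change or outlier counts were dropped. No passage promises either.
- The shift table follows the protocol, which has investigators interpret ECGs for clinical significance. It is also not the only ECG output, since a listing and the general post-treatment line exist too. Neither names QTcF.
- A reader might infer a neglected QT signal. The documents do not support that. Protocol 1.2.2.2 reports no relevant nonclinical effect on ECG or QT, Protocol 1.5 reports nothing clinically relevant on ECG in Phases 1 and 2, and QT is not among the SAP's adverse events of special interest. Nor do the ECG instructions (Protocol 6.7.7.1 and Appendix 11) ask for central reading, replicates or timing relative to dose, so these recordings were not set up to detect small QT effects.

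**Conclusion.** The point holds as a gap between protocol and SAP. A derivation that Protocol 6.7.7.1 assigns to the analysis has no counterpart in the SAP, and 7.7 does not disclose its absence. It should be corrected, because the correction is nearly free and a descriptive QTcF summary gives quantitative information that the shift table cannot.

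The consequence is limited to safety reporting. No efficacy test, alpha or sample size is affected, and nothing here suggests a QT problem with the drug. The half-width of about 2.0 to 2.6 ms depends on the assumed SD and on full arms of 450. It should not be read across to Week 24 or later.

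**What to change.** In SAP 7.5, add the derivation QTcF = QT/RR^(1/3) at each of the six scheduled ECG points (Screening, Weeks 12, 24 and 36, Week 52/ET, Post Treatment Week 4). Include it in the by-subject listing, and summarise value and change from baseline descriptively by arm and visit, as SAP 7.3 already does for vital signs. The ECG visit windows and the rules for choosing among continuous records are already in SAP 3.8.

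Counts of subjects above limits that the sponsor sets in advance would be a cheap addition. They would be a new analysis, not a restored commitment.

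If the sponsor prefers to omit QTcF, SAP 7.7 should say so and give the reason. If the ECG intervals turn out not to be held as data, that should be declared there as well.

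The cost is one derived variable, one extended listing and one or two descriptive tables, from measurements the protocol already requires. Declaring the omission costs one sentence.
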